ECMO management data will be collected daily for the first 28 days. Additionally, fluid balance, adverse events, Hb and all hematological data, anticoagulation management and monitoring will be collected every 24 hours.

Data will also be collected for the duration of mechanical ventilation, duration of ECMO, and ICU length of stay. Clinical outcome assessment will be made, with date of death, ICU discharge, hospital discharge, sixth month mortality.

Statistical Analysis

Descriptive statistics including frequency (percentage), median and interquartile range (IQR) will describe overall population and groups of survivors and non-survivors.

In order to describe current transfusion practice the amount of PRBC, Plasma and Platelets, will be described as units and ml and as a number of transfusions adjusted for ECMO length of stay and considering the concomitant bleeding episodes.

Fibrinogen and Antithrombin III will be described as mg or units respectively and as a number of administration.

Anticoagulation will be reported as type, mean dosage and the confidence interval (CI 95%).

Hb average level and the confidence interval (CI 95%) will be reported.

Baseline categorical and continuous variables will be compared for transfusion and ECMO weaning groups. In particular categorical variables will be compared with chi-square tests and continuous variables will be compared with Student's T-test, or Wilcoxon rank-sum tests, otherwise.

Multiple COX regression analysis will be used in order to explore the impact of confounding factors such as baseline patient severity, ECMO length of stay, bleeding episodes and possible others covariates and factors that will be observed and raised relevance during the first exploratory or univariate analysis. The impact of relevant confounding factors such as length of ECMO run, pre-ECMO severity scores, pre-ECMO administration of transfusions will be analyzed separately and together in multiple analyses.

In particular daily RBC transfusion will be studied according to the association to renal function, fluid balance, worst Hb level, episodes of bleeding, use of vasopressors, ECMO blood flow.

A p-value less of than 0.05 will be considered significant. Data handling and analyses will be done with SAS 9.4 software (SAS Institute Inc, Cary, NC, USA) and R 3.3 software (R Foundation for Statistical Computing).

Patient data Collection

For each included patient the investigators will collect the following data:

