1. Clinical data

- Demographics: age, gender, weight, height, BMI
- Pre-existing pulmonary disease: asthma, cystic fibrosis, chronic obstructive pulmonary disease, pulmonary hypertension, pulmonary fibrosis, chronic restrictive lung disease
- Main co-morbidities: diabetes mellitus, chronic renal failure, ischemic heart disease, heart failure, chronic liver failure, neurological impairment
- Cause of ARF: bacterial pneumonia, viral pneumonia, trauma/burns, aspiration pneumonia, pancreatitis, pulmonary vasculitis, post lung transplantation
- Diagnosis: ARDS, Chronic end stage respiratory disease
- Postoperative period < 7 days. Pregnancy or peri-partum.
- Pre-ECMO hospital/ICU length of stay, mechanical ventilation days
- Patient characteristics at ICU admission: SAPS 2, SOFA score, PaO₂/FiO₂ ratio, hematocrit, platelets
- ECMO severity scores: PRESERVE score, RESP Score, ECMOnet if appropriate

2. ECMO and daily management data

- Type of circuit: heparin-bonded or not, type of oxygenator
- Type of anticoagulation: heparin, bivalirudin, argatroban, no anticoagulant

- Dose of anticoagulation
- Amount of PRBC, Plasma, platelets transfused (unit and ml) the day before
- Eventual Fibrinogen administration (mg)
- Antithrombin III level
- Antithrombin III administration (Type: human plasma-derived, recombinant) and dosage
- Episodes of bleeding classified according to site (airway – including tracheotomy - oro-nasal, gastric, intrathoracic, abdominal, intestinal, retroperitoneal, urinary tract, other) and severity according to 5 adjusted categories of the Bleeding Academic Research Consortium (BARC) score: Type 0, no bleeding; Type 1, Any overt bleeding that requires heparin infusion rate reduction or PRBC transfusion (provided Hb drop was related to bleeding); Type 2, any overt bleeding that requires heparin infusion rate reduction and packed red blood cells transfusion or non-surgical procedure to stop bleeding (provided Hb drop was related to bleeding); Type 3, Any life-threatening bleeding that required PRBC transfusion and surgical intervention for control of bleeding or ECMO discontinuation; Type 4: any fatal bleeding
- Daily blood and air flow, ECMO FiO₂
- 24 hours diuresis and fluid balance
- Use of continuous renal replacement therapy
- Mean arterial pressure, use of vasopressors
- Septic shock
- Hemoglobin, hematocrit, platelet count, fibrinogen if available.
- Daily gas exchange: pH, PaO₂, PaCO₂, SaO₂

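### The Cox model names ECMO length and bleeding episodes as confounders without an event, time origin or time-updating; timed from cannulation, total ECMO length is not a valid fixed covariate and ever/never bleeding is biased

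*Combined protocol and SAP*

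**What the plan says.** Cox regression appears once in the combined protocol and SAP, under Statistical Analysis. The model is meant to "explore the impact of confounding factors such as baseline patient severity, ECMO length of stay, bleeding episodes", with other covariates to be chosen after univariate screening. The next sentence returns to run length, "The impact of relevant confounding factors such as length of ECMO run", and groups it with pre-ECMO severity scores and pre-ECMO transfusions. The following paragraph adds: "In particular daily RBC transfusion will be studied according to the association to renal function" and several other daily variables. It does not say by what model.

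No event, time origin, censoring rule or covariate coding is given. Several possible events are recorded. Data collection methods says: "Clinical outcome assessment will be made, with date of death, ICU discharge, hospital discharge, sixth month mortality", and item 4 of Patient data Collection adds ECMO weaning. Cannulation appears under Study duration, but only as the start of recording.

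Bleeding is graded in Study Design and again in item 2 of Patient data Collection. Type 1 is "Any overt bleeding that requires heparin infusion rate reduction or PRBC transfusion". Type 3 is "Any life-threatening bleeding that required PRBC transfusion and surgical intervention for control of bleeding or ECMO discontinuation". The top grade is "Type 4: any fatal bleeding". Item 2 also records "Amount of PRBC, Plasma, platelets transfused (unit and ml) the day before".

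**The concern.** Baseline severity is fixed at cannulation. Total run length and bleeding are not: both come into being during follow-up. A patient must stay alive and on ECMO to build up a long run or to have time to bleed. If either is entered as though known at time zero, that survival is credited to the covariate (immortal-time bias). Listing run length beside pre-ECMO items invites this handling, and nothing in the plan rules it out.

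The bleeding grade can also contain the outcome. Type 4 is fatal by definition, so it overlaps a death endpoint. Types 1 to 3 include PRBC transfusion among their criteria, so the same-day grade overlaps a transfusion endpoint.

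At stake are the association results, read at p < 0.05, in a study whose rationale is the benefits and risks of transfusion during VV-ECMO.

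**Working it through.** The plan gives no HR, event count or power for the Cox model, so there is no figure to reproduce.

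**Inputs from the document.** Mean run 12 days (Study Design). n = 2 × 100 = 200 (Study conduction: at least 100 in Italy, at least double worldwide). Significance level 0.05, taken as two-sided.

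**Assumed inputs.** 25-45% die on ECMO; bleeding 3-10% per ECMO day; later death 0.1-0.4% per day; weaning rates equal, or varying between patients (lognormal, log-SD 1, 1.5 or 2, recalibrated to the 12-day mean). The true effect is nil unless stated. HRs are medians over simulated cohorts of 200.

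**1. Total length, event = death on ECMO or weaning.** Patients leave the risk set when ECMO ends, so the patient with the event at time t has L = t and everyone else at risk has L ≥ t. Each partial-likelihood term is

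1 / Σ exp{β(L_j − t)}, with every L_j − t ≥ 0,

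which keeps rising as β falls towards minus infinity. In one simulated cohort the log partial likelihood was −325 at β = 0, −150 at β = −1 and −61 at β = −5. None of 9,600 fits converged for death on ECMO, and none of 9,600 for weaning.

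**2. Total length, event = later death.** Null HR per ECMO day:

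| Horizon | Equal weaning rates | Varying rates |
|---|---|---|
| 28 days | 0.951-0.963 (significant in 70-100%) | not run |
| 60 days | 0.980-0.987 | 0.994-1.003 |
| 180 days | 0.987-0.992 | 1.000-1.010 |

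Over both columns, false significance ranged over 1-55% of cohorts at 60 days and 1-75% at 180 days. A separate 28-day run with the same death hazard on and off ECMO (20-50% of runs ending in death) gave 0.92-0.94. Size and direction therefore depend on choices the plan leaves open. With the clock started at the end of ECMO among run survivors, the 180-day HR was 0.995-1.002 (significant in 2-6%).

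**3. Bleeding as fixed ever/never, event = death on ECMO.** This can be checked by hand for equal weaning rates. Let λ = 1/12 per day be the rate of leaving ECMO and b the bleeding rate. The mean run is 1/(λ+b) in never-bled patients and 1/(λ+b) + 12 in ever-bled patients. Under the null the same share dies in each group, so the crude death-rate ratio is the ratio of mean runs:

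- b = 0.03: 8.82 / 20.82 = 0.42
- b = 0.05: 7.50 / 19.50 = 0.38
- b = 0.10: 5.45 / 17.45 = 0.31

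The HR at day t is λ(1 − e^(−bt)) / {(λ+b) − λe^(−bt)}. It starts at 0 and never exceeds λ/(λ+b). At b = 0.05 and t = 12 it is (0.0833 × 0.451) / (0.1333 − 0.0457) = 0.43, with a ceiling of 0.625. A Cox fit gives most weight to the early days, so it falls below the crude ratio: 0.21-0.39 over all scenarios. At a true HR of 2 it gave 0.48-0.60.

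For later death the null HR was 0.80-0.86 (equal rates) or 0.97-1.54 (varying) at 60 days, and 0.84-0.91 or 1.02-1.59 at 180 days.

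**4. Time-updated bleeding.**

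- *Death on ECMO, lagged one day:* null HR 0.93-1.05 (significant in 2-8%); 1.80-1.94 at a true HR of 2.
- *60-day death, lagged, no on-ECMO status:* null HR 1.50-3.00. A second check gave 1.36-2.89 at 60 days, falsely significant in 25-100% of cohorts. Under these inputs the death hazard on ECMO is 0.25/12 = 2.1% to 0.45/12 = 3.75% per day, against 0.1-0.4% afterwards. Patients who have bled are more often still on ECMO, so bleeding stands in for being on ECMO.
- *60-day death, with time-updated on-ECMO status:* 0.94-1.05, and 0.93-1.07 in the second check.
- *If 10-20% of bleeds end ECMO (assumed), with status:* 0.99-1.00 when those patients take the usual post-ECMO hazard, and 1.07-1.21 when they keep the on-ECMO hazard for 7 days.

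**5. Type 4.** If 10% of ECMO deaths are coded Type 4 on the day of death (assumed), the null HR is 1.30-1.68. Lagged one day it is 0.97-1.06.

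**The case against.** The strongest reply is that the plan is under-specified and does not state an invalid model. The words total, fixed and from cannulation are not in the text. With the clock started at the end of ECMO, run length is a legitimate baseline covariate. That stands, and it is why the invalidity is conditional on timing from cannulation. But no such origin is stated, and listing run length with pre-ECMO items points towards cannulation.

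A model that fails to converge would be noticed. That also stands, so the death-on-ECMO and weaning cases are unlikely to reach print. The later-death models and the ever/never bleeding models fit without warning.

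Time-updating bleeding is not a complete remedy. For later death, without on-ECMO status, it is further from 1 than the ever/never coding it replaces. This stands in full and shapes the fix.

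The analysis is exploratory and has no powered hypothesis. That limits the severity but does not make a biased HR useful.

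A reader might infer that two analysts following this section would report opposite bleeding effects. The documents do not support that. The contrast would set one event and covariate set against another, and the highest later-death values need an extreme assumed spread of weaning rates. At log-SD 2 the median run is 3.8-5.6 days and 19-27% of runs last under one day, which nothing in the documents suggests.

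**Conclusion.** The concern holds in conditional form. The section names two post-cannulation quantities as confounders and leaves event, origin and coding open. Timed from cannulation, total ECMO length has no finite estimate for death on ECMO or weaning; that follows from the algebra, whatever the inputs. For later death its coefficient is distorted by an amount and direction that depend on the horizon and the weaning rates. Ever/never bleeding is biased strongly downward for death on ECMO (null HR about 0.2-0.4) and in either direction for 60-day or 6-month death. These sizes rest on the assumed death, bleeding and weaning rates and only illustrate them.

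The overlap of the bleeding grade with the outcome is real by definition, but it matters only if death or transfusion is the Cox event. The plan does not tie daily transfusion to the Cox model.

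It would be wrong to infer that the study's main result is compromised. The amounts of blood product used are descriptive and do not depend on this model. It should be fixed before analysis, as a matter of moderate weight.

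**What to change.** 1. Name the event and time origin of each Cox model.
2. Do not enter total ECMO length as a fixed covariate in a model timed from cannulation. Use it only in a landmark model that starts at the end of ECMO among patients who survive the run. Transfusions per ECMO day can stay in the descriptive tables.
3. For death on ECMO, enter bleeding (and PRBC, if it is the exposure) as time-updated from the daily records, lagged one day, with weaning as a competing event. Count the lag from the date of the event: PRBC is recorded for the preceding day, so form date and event date differ.
4. For 60-day or 6-month death, put time-updated on-ECMO status in the main model with time-updated bleeding. State as a limitation that Type 3 bleeding can itself end ECMO, so part of a bleeding effect may be removed or distorted.
5. If death is the event, do not count Type 4 as a covariate. If transfusion is the event, do not use the same-day severity grade.

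**Cost.** SAP wording and some programming, with no new data: bleeding and PRBC records, ECMO duration, weaning status and date of death are already planned. The lag attenuates slightly (a true HR of 2 for death on ECMO reads 1.80-1.94), and under the assumed inputs 7-13% of runs pass day 28, when daily records end. Separately, the recording schedule after day 14 needs reconciling: it is weekly in Study Design and Study duration, and daily to day 28 in Data collection methods.

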Study Design: international multicenter prospective observational cohort study.

For the primary outcome PRBC will be evaluated as total amount during the ECMO run and for the first 28 days as daily amount. The total amount of PRBC, adjusted for the ECMO length of stay, will be evaluated in light of pre-ECMO parameters (age, comorbidities, postoperative state and severity scores) and of daily data (bleeding episodes, ECMO blood flow, dieresis, CRRT, Hb, major events). Daily occurrence of PRBC transfusion will be described according to pre-ECMO characteristics and daily parameters (Hb, bleeding, hemodynamics, renal function, circuit change).

Plasma, platelets, Fibrinogen, Antithrombin III administration will be evaluated according to pre-ECMO data and according to daily APTT level (or other coagulation monitoring adopted), bleeding episodes, sepsis.

For the secondary outcomes type of anticoagulant will be described as well as daily dose and daily target for the parameter targeted (APTT, ACT, r-TEG, anti-Xa according to local protocol). Anticoagulation will be described in relation to pre-ECMO parameters and daily episodes of bleeding and occurrence of sepsis.

Bleeding episodes will be described according to site (airway – including tracheotomy - oro-nasal, gastric, intrathoracic, abdominal, intestinal, retroperitoneal, urinary tract, other) and classified according to severity following 5 adjusted categories of the Bleeding Academic Research Consortium (BARC) score: Type 0, no bleeding; Type 1, Any overt bleeding that requires heparin infusion rate reduction or PRBC transfusion (provided Hb drop was related to bleeding); Type 2, any overt bleeding that requires heparin infusion rate reduction and packed red blood cells transfusion or non-surgical procedure to stop bleeding (provided Hb drop was related to bleeding); Type 3, Any life-threatening bleeding that required PRBC transfusion and surgical intervention for control of bleeding or ECMO discontinuation; Type 4: any fatal bleeding.

The study is prospective and, consequently, in each center all consecutive adult patients who are eligible according to inclusion and exclusion criteria should be included in the study up to 20 patients.

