Every patient included will be registered for baseline values, and will then be followed for ECMO management and transfusion management daily for the first two weeks and weekly during the following two weeks or until ECMO weaning if the ECMO run will be shorter than the observation time. During the first two weeks of observation, daily parameters will be recorded. Moreover, data will be recorded for every PRBC, Plasma, Platelets transfusion event. The patients will be observed for the clinical outcomes until they are discharged from the ICU and 6-months mortality will be recorded. Considering that according to the Extracorporeal Life Support Organization summary, the average length of respiratory ECMO run is about 12 days we believe that the majority of ECMO run will be fully covered by the observation period and, at least, it will be paradigmatic of a center's actual practice and, at the same time, will assure a considerable sample size of transfusion events.

Data will be reported according to the STROBE (Strengthening the reporting of observational studies in epidemiology) statement checklist.

The knowledge about this topic may not be achieved differently by other study design like retrospective studies or surveys. In fact, in 2017, ESICM endorsed a survey on the topic (data presented at the ECISM congress 2018) that showed a strong variability among centers about blood products transfusions, but the level of evidence achieved by a survey is low. Moreover, to explore retrospectively datasets of published studies would not allow to highlight the current practice and the strength of the study rely on the length that is one year and will surely cover the current technological frame considering a rapidly evolving scenario.

Study population: inclusion criteria/patient selection

All patients who receive extracorporeal lung support (ECMO) for ARDS respiratory causes will be included. Of note, considering the observational design of our study, patients can be included in other studies concurrently (this will be noted on the CRF).

Exclusion criteria: refusal to include

Jehovah's witnesses and all patients refusing transfusions for personal reasons will not be excluded if a valid informed consent is acquired, but they will be analyzed separately.

Study conduction

The study will be conducted in compliance with the current Helsinki Declaration and the standards of good clinical practice.

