The protocol will be entered into a public database (www.clinicaltrials.gov).

Given the explorative nature of this study, the required number of patients was not calculated, but considering at least 10 patients/year for each center (considered the worst prediction) we imagine that the included patients will be at least 100 in Italy and we presume to enroll at least a double number worldwide.

Study duration

- Transfusions decisions for each patient will be recorded daily during a two-week period after ECMO cannulation and weekly for the subsequent two weeks, or until the end of ECMO support if the length is < 28 days.
- Patients will be observed until ICU discharge with a follow up to sixth months for mortality
- The inclusion period will be 12 months for each center.

Data collection methods

Data will be recorded using pre-printed CRF by the principal investigator (PI) in each center or directly they will be recorded online. All data will be reported in a centralized online and Web-based fully encrypted database (REDCAP). The study coordinator will regularly contact the local PI to ensure data collection and reporting as well as completion of patient follow-up.

Moreover the study coordinator, available at ISMETT, will keep regularly updated the local investigators on the data recorded and will help in keeping in touch with local PI or if authorized will keep in touch with eventual hospitals or other sanitary residency where the patients are transferred. In the management of the study the data manager available at ISMETT will be dedicated to the goal of reducing to the minimal the loss of data also with the follow up.

The access to the REDCAP database will be regulated by personal credentials (username and password) so that each investigator will have granted specific levels of access (read-only, data entry, or full-administrative privileges).

Every participating center will have to ask the permission to their Ethic Committee or other relevant and competent authorities according to the local rules.

Data will include clinical characteristics: baseline demographics, basic biological values (e.g., blood gas, hemoglobin), primary diagnosis, comorbidities, underlying etiology of acute respiratory failure, severity of illness (e.g., SOFA, SAPS 2), type of ECMO, and the size of the cannulas.

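### SOFA, PaO2/FiO2, hematocrit and platelets are recorded at ICU admission, with no value requested just before cannulation, although transfusion is to be analysed by pre-ECMO and baseline characteristics

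*Combined protocol and SAP*

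**What the plan says.** Patient data Collection, item 1 (Clinical data), has one line for "Patient characteristics at ICU admission: SAPS 2, SOFA score", which continues with the PaO2/FiO2 "ratio, hematocrit, platelets". The same list records "Pre-ECMO hospital/ICU length of stay, mechanical ventilation days", and on a separate line the ECMO-specific scores PRESERVE, RESP and ECMOnet.

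Elsewhere the baseline has no time attached. Study Design states "Every patient included will be registered for baseline values". Data collection methods lists blood gas and hemoglobin among the basic biological values, and "severity of illness (e.g., SOFA, SAPS 2), type of ECMO, and the size of the cannulas", again without a time point.

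On use, Study Design says that total PRBC, adjusted for time on ECMO, "will be evaluated in light of pre-ECMO parameters (age, comorbidities, postoperative state and severity scores"), and relates daily PRBC occurrence and the other blood products to pre-ECMO data. Statistical Analysis adds "Baseline categorical and continuous variables will be compared for transfusion and ECMO weaning groups". It also names baseline severity, pre-ECMO severity scores and transfusion before ECMO as confounders to be examined.

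**The concern.** A baseline covariate should describe the patient at time zero, which here is cannulation. An admission value does so only if little happens between admission and cannulation. A patient who deteriorates, bleeds or is transfused in the ICU before ECMO may start the run with a SOFA score, hematocrit and platelet count quite unlike those at admission.

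Hematocrit and platelet count at the start of ECMO are natural candidates for explaining how much blood is then given. If the comparison of transfusion groups uses older values, an association with the state at ECMO start may be blurred, and any adjustment that draws on those values may be incomplete. A table of such values presented as the pre-ECMO baseline would also mislead a reader about the patients' condition when support began.

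**Working it through.** The protocol states no figure that depends on this timing, so there is nothing to reproduce. The check sets the timing of each variable beside its use.

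**1. Time zero.** The Summary and Study duration both count observation from cannulation.

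**2. Timing of each variable.**

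| Variable | Time in the itemised list | Any other value in the protocol |
|---|---|---|
| SOFA | ICU admission | None timed before cannulation |
| PaO2/FiO2 | ICU admission | Baseline blood gas, no time; daily gas exchange on ECMO |
| Hematocrit (Hb) | ICU admission | Baseline hemoglobin, no time; daily Hb and hematocrit on ECMO; Hb before a PRBC transfusion, where available |
| Platelets | ICU admission | Daily count on ECMO |
| SAPS 2 | ICU admission | None |
| PRESERVE, RESP | Not stated | Called pre-ECMO scores in Predefined subgroup analyses |

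The daily haematology belongs to item 2, ECMO and daily management data. The first entry there is not stated to precede cannulation.

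**3. Can admission and cannulation differ in time?** Yes, on three pieces of the plan's own text. It collects pre-ECMO hospital/ICU stay and ventilation days. The Background describes ECMO as salvage when gas exchange fails despite protective ventilation and other rescue therapies. Statistical Analysis lists transfusion before ECMO as a confounder, so blood is expected to be given before the run. In a patient transfused between admission and cannulation, the admission hematocrit no longer describes the start of ECMO.

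**4. Which analyses are exposed?**
- Exposed: the comparison of baseline variables between transfusion groups and between weaning groups; the description of transfusion by pre-ECMO characteristics, so far as it uses these values; and any model in which baseline severity means SOFA, or in which hematocrit or platelets enter after the univariate step.
- Not exposed: daily and total amounts of blood products as description; the daily RBC analysis, which uses the worst Hb; the centre trigger profile from repeated Hb; and the subgroup by PRESERVE and RESP quartiles.

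**5. Could the admission values be taken on ECMO?** Study population restricts neither the place nor the time of cannulation, and the list does not say whether the referring ICU or the study ICU is meant. If it is the study ICU, a patient who arrives already cannulated would have on-circuit values entered as baseline. No listed item flags such a patient explicitly.

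**6. Size.** A calculation would need the distribution of time from admission to cannulation, the correlation between admission and pre-cannulation values, and the share of patients cannulated before admission. The documents give none of the three.

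**The case against.** The strongest reply is that the plan does not rest its severity adjustment on this line. Predefined subgroup analyses identifies the pre-ECMO severity scores as PRESERVE and RESP, and the same phrase in Statistical Analysis can be read that way. Hematocrit and platelets are not named as adjustment covariates; the pre-ECMO parameters listed for total PRBC are age, comorbidities, postoperative state and severity scores. Values nearer the transfusion decision are collected daily and around PRBC transfusions. The age of the admission values can be reported, because the pre-ECMO stay is recorded. SAPS 2 is properly an admission score.

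Most of this stands and narrows the point, but it does not remove it. The identification of the scores appears only in the subgroup section. Baseline severity in the Cox model is tied to no score, and Data collection methods gives SOFA and SAPS 2 as its examples of severity. Hematocrit and platelets are still baseline variables to be compared between transfusion groups, and they may enter models after screening. The recorded stay shows how old a value is without supplying the current one. Values taken during ECMO may already reflect the circuit or a transfusion, so they are not a clean baseline.

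**Conclusion.** The point holds in a limited form. The plan fixes four variables that change over time (SOFA, PaO2/FiO2, hematocrit, platelets) at a moment that may precede time zero, asks for no later pre-cannulation value, and then analyses transfusion by pre-ECMO and baseline characteristics. The effect falls on the secondary layer of comparisons and models; the descriptive core of the study is intact. For a patient cannulated on the day of ICU admission there may be almost no difference.

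A reader might infer more, and the documents do not support it:
- That many patients have on-circuit baselines. This is possible under the eligibility rule, but the protocol neither describes such patients nor indicates their number.
- That a stated fraction of confounding is left uncontrolled. Any such figure would rest on an assumed correlation, and the plan does not commit to adjusting for hematocrit or platelets.
- That early- and late-cannulating centres cannot be compared. The planned centre strata are workload and geography, and no planned centre comparison is stated to rest on admission hematocrit.
- That severity adjustment fails throughout. If PRESERVE and RESP are the scores meant, adjustment for them does not depend on admission SOFA or SAPS 2.

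**What to change.** - Add to the CRF the last value before cannulation, within a stated window (for example 24 hours), for SOFA, PaO2/FiO2, Hb/hematocrit and platelets. Use these in the baseline comparisons and in any baseline adjustment.
- Keep SAPS 2 at ICU admission as its own item.
- State which ICU admission is meant, and add a yes/no item for cannulation before admission to the study ICU.
- State in Study Design and Statistical Analysis that PRESERVE and RESP are the pre-ECMO severity scores.

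The cost is a change of CRF wording and a few more routine values per patient. Some will be missing for patients cannulated elsewhere and should be reported as missing, not replaced by on-circuit values. The change is best made before enrolment, since values held at a referring hospital may be hard to recover later.
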